Fold change will be the primary immune analysis and will be calculated for each individual subject based on their day 0 spot forming units on ELISPOT assay. Fold change will be calculated at each time point (chemo initiation, during chemo, 3 months post). This will take place in both the vaccinated and control (non-vaccinated) groups. The control group will have responses measured as well and is the essential comparison group to see how the responses change in relation to the vaccinated group through the pre, during, and post chemotherapy time points. As this model reflects a 2 group by 3 time point design, our initial overall assessment of the data will use a 2X3 Repeated Measures ANOVA (RMANOVA) to identify mean differences between groups, within time mean differences, and the interaction between groups and time to identify if the trends in the means over time is different for groups (vaccine vs. no vaccine). For the next step to gain a better understanding of how well the vaccine works at each time point (Hypothesis 2-4), we will use independent samples t-tests to analyze group mean differences at each time point separately to gain a better understanding of how the groups may be different at chemotherapy initiation, during chemotherapy, and at 3-24 months post-chemotherapy. Additionally, if we identify a significant interaction between group and time points, we will run follow-up RMANOVAs for each group separately to identify not only mean difference over time, but also linear (e.g. a steady increase or decrease in mean scores over time) and quadratic (e.g. a high mean scores at chemotherapy initiation, followed by a decline in mean score during chemotherapy, followed by a steady increase in mean score at 3-24 months post-chemotherapy) trends in the

means over time for each group. Violations of the assumptions for each analysis will be tested and the data will be transformed or the nonparametric equivalence analysis will be used when appropriate.

We will also perform multiparameter flow cytometry analysis on the cells to measure in greater detail what subtypes of T cells are responding. If there are sufficient PBMC available we will perform transcriptomic analysis of vaccine-induced gene changes over the time course of the study. Antibody titers may also be assessed as they are of historical interest in zoster and there is significant data on changes in antibody titers as at least a measure of immunologic response.

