The subjects chemotherapy is decided by the Oncologist and/or Tumor Board in consultation. The duration of chemo similarly is also decided clinically. If the patient needs surgery or XRT

as part of the therapy, it is decided on entirely by the clinicians. The study is working around all of these clinical decisions.

Subjects will be called between visit 2 and 3 and then between visits 3 and 4. They will be asked if they had a side effects or event that may have been serious since the last study visit or telephone contact. They will also be asked if they were exposed to anyone who has chickenpox or shingles, and if they had any symptoms of shingles.

For 4 weeks after they receive their shot, they will be asked to record information about potential vaccine side effects on the vaccination Report Card.

14. Will the research involve the following?

N/A Chart/Data Review

Placebo Group No Yes (describe):

Other Control Group No Yes (describe): The control group is persons that do not get the vaccine.

Randomization No Yes (describe): We will obtain clinical information to determine eligibility this includes meds and PMH and then follow the subject's clinical course to know when to do the subsequent sampling. We will use a cloud based randomized tool to generate the list before the start for the whole study for what the order of vaccine or no vaccine will be. We will then have paperwork packets in the order of enrollment premade. We will open each packet at the consenting time and find vaccine or not and enroll and begin the study.

Deception No Yes (describe):

15. Does the research involve the use and/or disclosure of Individually Identifiable Health Information in any form or medium?

No Yes If yes, complete the required HIPAA Waiver/Authorization forms.

16. Does the study include the administration of a study agent that does not require FDA approval and does not require an IND (e.g. vitamins, food supplements, isotope tracers, alternative medicines, etc.)?

No Yes -provide a detailed description of the procedures used to assure patient safety:

17. Will radioactive material be administered or will subjects be exposed to ionizing radiation?

• Ex. Radiographic equipment, fluoroscopic equipment, and CT scanners, etc.

No Yes

18. In your judgment, could the objectives of the research be met in a way that presents less risk to subjects?

No Yes please explain:

Section 4 – Subject Selection, Recruitment, and Vulnerable Populations

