38. Please list by bullet and describe the reasonably foreseeable physical, psychological, social, economic, and privacy risks, side effects, or discomforts associated with the research and their expected frequency and severity.

- *If this study is a retrospective chart review, or involves only the analysis of data, risk may still be present in the form of data security concerns.*

Some reported risks of ZOSTAVAX include:

- o Injection site reactions such as: local redness, swelling, pain and tenderness, itching, bruising, and warmth.
- o Headache
- o Fever
- o Allergic reaction, which may be life-threatening

- o Rash, which may resemble chickenpox
- o Swollen glands near the injection site (may last a few days to a few weeks)
- o Joint pain
- o Muscle pain

These reactions are either rare or mild in severity making this a safe vaccine with very few exclusions by the FDA.

Blood samples: drawing blood from your arm may cause pain, bruising, lightheadedness, and rarely, fainting or infection.

Loss of privacy is always a risk with any study. We are not collecting those most sensitive topics of information and we will code the sample as soon as they are enrolled so these risks are minimal.

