- The consent form and other information presented to potential research subjects adequately and clearly describe confidentiality risks.
- The informed consent process and the informed consent document, and if applicable the Authorization Form, clearly delineates who will have access to the subject's information and under what circumstances data may be shared (i.e., government agencies, sponsors).

53. Describe when and where subjects will provide their information. Include the nature of the information and who will receive and use the information. Document the provisions used to protect privacy interests of those subjects when gathering their information and data.

We will obtain the information from CPRS and from the subjects in an exam room or hospital room. We will obtain birthdate, PMH, and information on how to contact the person as the study is ongoing. The link to the code will be stored in a password protected file behind the VA firewall and in paper form in a locked cabinet in a locked room.

54. Will researchers have access to identifiable private information about potential subjects outside of this research project? *Ex. PI is provider who has access to medical records for clinical care*

- No **Yes- please explain:** The oncology CO-I's on the study are providers for the subjects.

55. Will Researchers collect identifiable private information on anyone other than the subject?

- *Ex. family members, friends, colleagues, classmates...etc.*

No Yes -please explain:

56. At the time data are transcribed or recorded for this study they are?

Fully identifiable- list identifiers to be collected:

Coded with a unique identifier- describe the code: It will be a few letters and numbers. We will not use the subjects S.S. number, birth date or initials for the code.

a. Who will have access to the key? All of the study team.

b. Where is the key maintained? Two locking barriers must be in place between the coded data and the key. We will have a password protected file behind the VA firewall and also a written backup stored in a locked drawer or cabinet in the oncology office area initially as the enrolment is ongoing and then for long term moved to [name] lab in K203.

De-identified-by Privacy Officer or Statistician.

Other (describe):

57. How will electronic research data be secured while the study is active?

No electronic data will be stored

VA encrypted laptop

Encrypted VA device/media- describe:

VA network drive;

M: drive; whose?

S: drive

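### Coding the samples does not ensure that those reading the primary ELISPOT endpoint are masked to arm, and nothing else in the plan does so

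*Protocol*

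**What the plan says.** - **Endpoint.** Protocol item 10 makes fold change the primary immune analysis, "calculated for each individual subject based on their day 0 spot forming units on ELISPOT assay". SAP section 2.7 agrees.
- **Control.** Item 14: "The control group is persons that do not get the vaccine". The same item has staff open a pre-made packet at consent and learn the arm from it.
- **Who may consent.** Item 50 authorizes every member of the study team.
- **Who holds the key.** Item 56a: "Who will have access to the key? All of the study team". It makes no exception for laboratory staff, plate readers or the statistician.
- **Where the key is.** Item 56b describes a password-protected file and "a written backup stored in a locked drawer or cabinet in the oncology office area initially as the enrolment is ongoing", "then for long term moved to [name] lab in K203".
- **Why samples are coded.** Item 38 gives privacy as the reason: "we will code the sample as soon as they are enrolled so these risks are minimal".
- **Where ELISPOT is run.** Item 10 lists what goes to outside laboratories: T-cell marker work and cloning, transcriptomics and an anti-glycoprotein ELISA. ELISPOT is not on that list. Item 5 has Duke's coded samples coming to Cleveland for analysis alongside the local ones. This implies, without stating it, that the Cleveland team runs ELISPOT.
- **Masking.** Neither document mentions masking of assay staff or readers.

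**The concern.** Subjects and clinic staff know who was vaccinated, so masking the assay is the main safeguard left for the primary endpoint. The sample codes look like that safeguard. Under the written rules, though, a team member who ran plates could also have opened the subject's packet, or could look the subject up in the key, without departing from the protocol.

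If setting spot thresholds, excluding artefacts or repeating wells involves judgement, knowing the arm and visit could push post-vaccination counts up or control counts down. That would produce a group difference in the direction of hypotheses 1 to 4, and enrolling more subjects would not remove it. Both documents say the pilot data will inform the size of a later study, so the distortion could carry forward.

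**Working it through.** **1. Can assay staff learn the arm under the written rules?**

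| Route | Rule | Closed for ELISPOT readers? |
|---|---|---|
| Allocation packet | Item 14 (opened at consent) with item 50 (anyone on the team may consent) | No |
| Code key | Item 56a (whole team) | No |
| Tube labels and plate maps | Not described | Not stated |
| Duke key | Holder not stated (item 5) | Not stated |

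The first two routes are open to any reader who belongs to the study team. The packet reveals the arm directly. The key links code to person; the documents do not say whether it also lists the arm.

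**2. The plan's own figures.** No stated figure depends on masking, and masking changes none. For reference, 90 × 0.85 = 76.5, which agrees with about 76 analyzed, or 38 per arm. With 38 per arm, α = 0.05 and power 0.80, the smallest detectable standardized difference for a t-test is 0.576 one-sided and 0.651 two-sided. The stated 0.58 therefore matches a one-sided test, although the documents do not state sidedness.

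**3. Illustration of size.** Two inputs are assumptions that the documents do not supply: reading drift of 10–20% between arms, and an SD of log10 fold change of 0.3–0.5.

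Shift in SD units: b = log10(1 + drift) / SD.
- Smallest: log10(1.1)/0.5 = 0.0414/0.5 = 0.083.
- Largest: log10(1.2)/0.3 = 0.0792/0.3 = 0.264.

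Rejection probability with no true effect: noncentral t, df = 74, noncentrality b × √(38/2).
- b = 0.083: noncentrality 0.36, two-sided rejection 6.5%.
- b = 0.264: noncentrality 1.15, two-sided rejection 20.6%.

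**4. If only Cleveland's samples are exposed.** Cleveland is 60/90 = 2/3 of enrolment, so the average shift is 2/3 of the above: 0.055 to 0.176 SD. Rejection is then about 6% to 12%.

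**5. Free of the drift and SD assumptions.** For a shift of 0, 0.1, 0.2 or 0.3 SD, two-sided rejection is 5.0%, 7.1%, 13.8% or 25.2%. One-sided it is 5.0%, 11.3%, 21.7% or 36.3%. If readers cannot know the arm, reading drift cannot depend on it and the rate returns to 5%.

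**6. Limits.** These rates are for one t-test on the log scale. The plan starts with a 2 × 3 repeated-measures ANOVA and transforms data only if assumptions fail. A drift equal at all three visits would, on the log scale, move the group main effect but not the group-by-time interaction.

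**The case against.** Item 56 answers a privacy question about who can link a code to a person. It is not a blinding plan, and reading it as proof that readers are unmasked goes too far. The documents do not name the readers, place them in the study team, or say that the key shows the arm. That stands: the supported statement is that masking is not ensured, not that it is absent in practice.

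A reader might also infer from the key's later move to K203 that it will sit in the ELISPOT laboratory. The documents do not support this. The paper copy stays in the oncology area during enrolment and moves for long-term storage. Laboratory names are removed, and the timing of the assays is not given. Item 59 does allow study data in K203 earlier, but in a locked cabinet, and the form requires two locking barriers between key and coded data. Locks, however, do not restrict people who are entitled to open them, so the whole-team access rule remains.

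Three further points stand in part:
- Nothing gives Cleveland readers the Duke key, so up to 30 of 90 subjects may be unaffected.
- Fold change is a ratio to day 0. Drift that scales all of a subject's samples equally cancels, so bias needs the reader to know, or be influenced by, the visit as well as the arm.
- The counting method is not described. Automated counting, fixed thresholds or duplicate reading would also reduce the risk, so masking is not the only protection available.

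None of these supplies masking. They limit how firmly its absence can be asserted and how large the effect might be.

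**Conclusion.** The point holds as a missing protection. With a no-vaccine control, key access for the whole team, consent by any team member and no masking of assay staff, the coded samples do not ensure that the primary endpoint is read without knowledge of arm. It rests on one inference, that ELISPOT is run by the Cleveland team, which items 5 and 10 imply.

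The size is unknown. The ranges of about 6–21% (all samples exposed) and about 6–12% (Cleveland only) show what modest drift could do with 38 per arm. They are not estimates, because neither the drift nor the SD is in the documents. The change is worth making even in a pilot, because it is cheap and the samples are already coded.

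**What to change.** - **Item 56a:** replace whole-team access with a short list of roles that do no assay work, such as the coordinators who schedule visits.
- **Items 10 or 13, and SAP section 2.7:** state that staff who run or read ELISPOT, or who accept, repeat or reject wells, have no access to the key, the allocation packets or the arm until spot counts are locked.
- **Item 50:** bar those staff from obtaining consent until the lock. Without this, restricting the key leaves the packet route open.
- **Labels and storage:** keep arm off tube labels and plate maps, and keep the paper key away from assay staff until the lock, wherever it is stored.
- **Duke:** state who holds that key and apply the same rule.

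If some readers cannot be masked, the protocol should say so. The cost is a small separation of duties, which may be felt in a small team, and sample-identity queries must go through a coordinator. No additional assays or subjects are needed.

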****If yes complete the following:**

a. LSCDVAMC investigator will receive:

- Hardcopy information or specimens
 Electronic information

b. What are the procedures for transporting and/or transmitting identifiable information securely?

c. What will be the final disposition of the identifiable data transferred to the LSCDVAMC?

- Record Control Schedule 10-1 indicates that all research records must be retained indefinitely

61. Is identifiable information physically or electronically sent **FROM** the LSCDVAMC to other institutions or locations?

- No Yes contact Privacy Officer [name] or [name] [contact] / [contact] [contact] / [name] or Information Security Officer [name] [contact] / [contact] – prior to submitting to the Research Service

****If yes complete the following:**

a. The LSCDVAMC investigator will send:

- Hardcopy information or specimens
 Electronic information

b. What are the procedures for transporting and/or transmitting identifiable information securely?

c. What will be the final disposition of the identifiable data transferred offsite?

- Record Control Schedule 10-1 indicates that all research records must be retained indefinitely

Records will be maintained indefinitely or until the RCS-10 is updated.

62. Record Control Schedule 10-1 indicates all research records must be retained indefinitely. Please indicate where this information will be stored and the safe guards to protect it:

a. Electronic Safeguards:

- No electronic data will be stored
 VA encrypted laptop
 Encrypted VA device/media- describe:

- VA network drive;
 - M: drive; whose?
 - S: drive
 - Folder access password protected
 - Other drive location (for example P: drive):
 - Folder access password protected

b. Hardcopy safeguards. Two locking barriers must be in place.

- No hardcopy data will be stored
- Locked Office and Locked File Cabinet
- Coded by Study Staff
- De-identified by Privacy Officer or Statistician
- Other- Describe:

Facility name, address, and room number where hardcopy or electronic data will be stored:

For long term storage the paper will go to Wade Park VA, K203, [name] in a locked cabinet in [name] laboratory.

Section 8 – Data and Safety Monitoring – Greater than Minimal Risk Study

- For all research that is greater than minimal risk a Data and Safety Monitoring Plan must be developed.
- This is a plan to assure the research includes a system of appropriate oversight and monitoring of the conduct of the study to ensure the safety of subjects and the validity and integrity of the data.

*CHECK BOX IF THIS IS A MINIMAL RISK STUDY SKIP TO #65

63. Safety monitoring for this greater than minimal risk project will include:

- Data Safety Monitoring Board:
- Data Monitoring Committee
- Other

- *Attach the plan or provide details including whether committee is independent from the study sponsor, how often it meets, whether written reports are available, etc*

The PI, primary Co-I's, and Coordinators of the study (Cleveland and Duke) will correspond at least monthly and review the study and vaccine report cards for any sign of increased toxicity in this population.

64. Describe the plan for on-site data monitoring by the sponsor, contract research organization (CRO), or other independent body: The sponsor will monitor the study according to

FDA and industry standards, with details of the monitoring activities to be made available to the IRB once they are available.

- *Research Office must be notified of all on-site monitoring visits.

65. Conditions that may result in removal of subjects from the research (check all that apply):

- | | |
|---|---|
|  Medical condition unchanged |  Medical condition worsened |
|  Serious adverse event |  Intolerable complications |
|  Pregnancy |  Investigator's clinical judgment |
|  Subject withdrawal |  Subject uncooperative or noncompliant |
|  Study closure by sponsor or FDA |  Refusal to suspend breast-feeding |
|  Other-describe: |  Not Applicable |

66. If a subject withdraws or is removed from the study, describe the potential risks of early withdrawal and the procedures in place to minimize these risks:

There are no risks to early withdrawal from the study.

Section 9 – FDA-Regulated Drugs/Biologics

NOTE: If this research involves the use of any drugs or biologics, the study is subject to the Food and Drug Administration (FDA) regulations.

- Documentation of FDA approval for the experimental use of these agents must be provided for review (industry sponsored protocol listing the IND number, letter from the FDA, letter from industry sponsor, or other document and/or communication verifying the IND for this study).
- All drug/biologic products must be dispensed and tracked through the LSCDVAMC Research Pharmacy.
- An M.D. must be part of the Research Team for all studies that involve the use of a device or drugs.
- The LSCDVAMC Pharmacy and Therapeutics (P&T) Committee must approve: (1) Studies of investigational drugs (2) research involving an FDA-approved drug used in a non-approved manner, and (3) an FDA-approved drug, used as approved, when its use is part of a research protocol.
- VA Form 10-9012 Investigational Drug Information Record –must be completed for each drug being evaluated in a research study, regardless of IND status. In addition, the VA Form 10-9012 provides a listing of all authorized prescribers for the study drug(s).

67. Type of Product- check all that apply:

- Not Applicable -No FDA-regulated drugs/biologics involved – Proceed to Section 10
- Drug
- Biologic or Other: ZOSTAVAX (shingles vaccine)

68. Type of Trial (check as applicable):

- Phase I Phase II Phase III Phase IV NA

Phase I Trials: Initial studies to determine the metabolism and pharmacologic actions of drugs in humans, the

side effects associated with increasing doses, and to gain early evidence of effectiveness; may include healthy subjects and/or patients.

Phase II Trials: Controlled clinical studies conducted to evaluate the effectiveness of the drug for a particular indication or indications in patients with the disease or condition under study and to determine the common short-term side effects and risks.

Phase III Trials: Expanded controlled and uncontrolled trials after preliminary evidence suggesting effectiveness of the drug has been obtained, and are intended to gather additional information to evaluate the overall benefit-risk relationship of the drug and provide adequate basis for physician labeling.

Phase IV Trials: Post-marketing studies to delineate additional information including the drug's risks, benefits, and optimal use.

69. FDA Status of Drugs/Biologics –

*** For drugs, an IND may not be necessary if ALL seven of the following conditions are met:**

1. The drug being used in the research is lawfully marketed in the United States;
2. The research is not intended to be reported to FDA in support of a new indication for use or to support any other significant change in the labeling for the drug;
3. The research is not intended to support a significant change in the advertising for the product;
4. The research does not involve a route of administration or dosage level, use in a subject population, or other factor that significantly increases the risks (or decreases the acceptability of the risks) associated with the use of the drug product;
5. The research is conducted in compliance with the requirements for IRB review and informed consent (21 CFR parts 56 and 50, respectively);
6. The research is conducted in compliance with the requirements concerning the promotion and sale of drugs (21 CFR 312.7);
7. The research does not intend to invoke 21 CFR 50.24 (Exception from informed consent requirements for emergency research).

Provide the following information for each drug/biologic used in this study:

Trade and Generic Name	Manufacturer	FDA Approved	Product use consistent with product labeling	IND Required*	IND Number	IND Sponsor or Holder**
ZOSTAVAX	Merck	y	Y	N		

70. **When the PI holds the IND, complete the following:

i. The PI has reviewed the Guidance on Requirements of the Sponsor and the Investigator as Sponsor

Yes

ii. As the PI, you will comply with the regulatory responsibilities of a sponsor

Yes

71. Drug Information for each drug listed in the protocol -check as applicable.

Approved Drugs

Not Approved

- **Attach VA Form 10-9012 Investigational Drug Information Record for each drug used in the protocol**
- **Attach Package Insert or PDR monograph – copy ready, 8.5 x 11 for each drug listed in the protocol**
- **Attach Investigator’s Brochure**

72. Provide a detailed description of how FDA-regulated drugs/biologics will be stored, secured, dispensed, administered, tracked, and returned.

The vaccine needs to be stored frozen and is resuspended by the researcher or clinical staff right before use as specified in the package insert. We will store the vaccine in the research pharmacy and can track its use from there.

Section 10 – FDA-Regulated Devices

This section should be completed for a medical device that is the subject of a clinical study designed to evaluate the effectiveness and/or safety of the device.

- An investigational device may be an FDA approved device that is being studied for an unapproved use or efficacy. This also includes an approved device that is being studied for an unapproved or approved use in a controlled, randomized, or blinded clinical trial.
- Documentation of FDA approval for the experimental use of the device must be provided for review (industry sponsored protocol listing the IDE number, letter from the FDA, letter from industry sponsor, or other document and/or communication verifying the IDE for this study).

Device Risk Determination:

Significant Risk (SR) Device is an investigational device that: (1) is intended as an implant and presents a potential for serious risk to the health, safety, or welfare of a subject, or (2) is purported or represented to be for a use in supporting or sustaining human life and presents a potential for serious risk to the health, safety, or welfare of a subject; or (3) is for a use of substantial importance in diagnosing, curing, mitigating, or treating disease, or otherwise preventing impairment of human health and presents a potential for serious risk to the health, safety, or welfare of a subject; or (4) otherwise presents a potential for serious risk to the health, safety, or welfare of a subject.

Non significant Risk (NSR) Device is a device other than a significant risk device.

The IRB is required to document the basis for risk determination based on the proposed use of a device in the research by considering the nature of the harm that may result from the use of the device. FDA has the ultimate decision in determining SR and NSR.

An M.D. must be part of the Research Team for all studies that involve the use of a device.

The Environment of Care Committee (EOC) must approve all research that involves electrically line-operated devices, which have leads or electrodes and will come in contact with human subjects.

73. Type of Product-check all that apply:

- Not Applicable -No FDA-regulated devices involved – Proceed to Section 11)**
- An FDA regulated device will be used BUT not with intent of studying safety or efficacy (Proceed to Section 11)**
- Device**

74. List the device-include name and manufacturer:

75. FDA Regulatory Status of the Device:

FDA Approved Device

- A device approved by the FDA for distribution, marketing, sale to, and use by, the public for the study's indication.

New Indication of an FDA Approved Device

- A device NOT approved by the FDA for distribution, marketing, sale to, and use by, the public for the indication used in the study.

Investigational - Investigational Device Exemption (IDE)

- An FDA designation that permits a manufacturer to lawfully ship an unapproved device for use in a research study.

Provide the following:

- a. IDE Number:
- b. IDE Sponsor or Holder:

If the PI holds the IDE, complete the following:

- i. The PI reviewed the Guidance on Requirements of the Sponsor and the Investigator as Sponsor

Yes

- ii. As the PI, you will comply with the regulatory responsibilities of a sponsor

Yes

- c. FDA or Sponsor Device Risk Determination

Non-Significant Risk

Significant Risk

- d. Attach documentation of FDA approval for the experimental use of the device (industry sponsored protocol listing the IDE number, letter from the FDA, letter from industry sponsor, or other document and/or communication verifying the IDE for this study).

Humanitarian Use Device (HUD)

- An FDA designation for a medical device intended to benefit patients in the treatment or diagnosis of a disease or condition that affects or is manifested in fewer than 4,000 individuals in the United States per year. For more information about Humanitarian Use Devices see the HRPP SOP manual on the R&D website.

Provide the following:

- a. HUD Number:
- b. HUD Sponsor or Holder:
- c. Include a copy of the FDA letter granting Humanitarian Use Device (HUD) status.

510(k) Status –

- A device determined by the FDA to be “substantially equivalent” to an existing device that is legally marketed in the U.S. Until a 510(k) device is approved, it is still considered investigational.
- a. Provide the name of an equivalent device and sufficient documentation to justify 510(k)

76. Attach device information (i.e., brochure, device label)

77. Provide a detailed description of how FDA-regulated devices will be stored, secured, dispensed, administered, tracked, and returned.

Section 11 – Genetic Testing and Discovery of Genetic Information (DNA)

78. Does the research involve genetic testing or DNA/RNA extraction?

No genetic testing (*Proceed to Section 12*)

Yes- complete the following:

a. Describe the purpose of the genetic testing component of the study

- *Is it to establish risks, associations, or prevalence?*

b. Describe whether the test is a standard test already in clinical use or a new or experimental laboratory study

c. Describe the accuracy of the test

- *Sensitivity, specificity, reliability, validity, and variability*

79. Does an abnormal test result indicate that the subject:

- Has a specific condition
- Is at risk for a specific condition
- May be at risk for a specific condition
- Has, is, or may be at risk for some other outcome
- Other (*describe*):

80. Does a normal test result indicate that the subject

- Is not at risk for a specific condition
- Is at a lower risk for a specific condition
- Is at a population risk for a specific condition

81. Is there a risk of discovery of other results such as non-parentage or other genetic conditions?

- No Yes- please explain:

82. Will test results produce information on anyone (e.g. a first-degree relative) besides the subject?

No Yes- please explain:

83. To whom and in what manner will genetic information be reported?

84. Will genetic counseling be made available to subjects?

No Yes- indicate who will conduct the counseling and whether there are any additional charges:

85. Will DNA samples be stored?

No Yes--describe where, how, and for how long the samples will be stored:

86. Who will own the DNA samples?

87. Will there be any subsequent analysis of the DNA samples?

No Yes- describe the purpose of the subsequent analysis and whether there will be dissemination of any new information:

88. Describe how samples will be handled if the subject withdraws consent for further participation:

89. Will the samples be distributed to other investigators?

No Yes- please explain:

90. Describe the provisions to maintain the confidentiality of research data, especially in cases where data can be linked to individual subjects:

Section 12 – Tissue Collection/Storage/Banking*

It is VA policy to ensure that human biological specimens, as well as the linked data collected as part of research projects conducted by VA investigators in VA facilities or approved off-site locations, are maintained at *VA approved tissue banks or VA-sponsored tissue banks.

See VHA Directive 2000-043 "Banking of Human Research Subjects' Specimens" for more information and also visit http://www.research.va.gov/programs/tissue_banking/default.cfm

Human biological specimens (specimens).

- Human biological specimens are materials, such as blood, urine, tissue, organs, hair, nail clippings, buccal swabs or any other materials that are derived from human subjects and are

either collected specifically for research purposes or as residual specimens from diagnostic, therapeutic or surgical procedures.

91. *Does the research involve storage or banking of human specimens or identifiable private information for use in future studies? (check all that apply)

No (proceed to Section 13) Yes-describe status of VA approved or VA sponsored facility:

Storing or banking identifiable private information

Storing or banking human specimens

Please provide the following information:

- a. What identifying information will be required?
- b. What are the foreseeable uses of the specimens (e.g., research, pharmaceutical products, production of cellular lines for various uses, etc.)?
- c. What is the VA approved or VA sponsored location/institution where the information and/or specimens will be stored?
- d. How long will the information and/or specimens be stored?
- e. Is the storage facility an on-site or off-site location?
- f. Will subjects be able to request that their specimen and/or information be withdrawn from the bank or repository? (explain)

Section 13 – Children as Research Subjects

Research involving children must not be conducted by VA investigators while on official duty or at VA or VA-approved offsite facilities unless a waiver has been granted by the CRADO (See VHA Directive 2001-028 "Research Involving Children" for more information.

92. Do you plan to enroll children as research subjects?

No (Proceed to Section 14)

Yes- Age range of subjects:

93. Category of Research (Check the box next to the category of research you believe your research falls under. The IRB will make a final category determination during review.):

Research involving minimal risk (the probability & magnitude of harm or discomfort anticipated are not greater than those ordinarily encountered in daily life or during routine physical or psychological tests.) (46.404)

Research involving greater than minimal risk but of potentially direct benefit to the subject. (46.405)

Research involving greater than minimal risk and no prospect of direct benefit to the subject but likely to yield generalizable knowledge about the subject's disorder or condition. (46.406)

Research not otherwise approvable which presents an opportunity to understand, prevent or alleviate a serious problem affecting children/decisionally impaired adults. (46.407)

94. Do you anticipate enrolling minors who are wards of the state?

No Yes

95. Permission of parents or guardian (*check one only*):

The permission of each child's parents or guardian will be sought unless one parent is deceased, unknown, incompetent, or not reasonably available, or when only one parent has legal responsibility for the care and custody of the child (required for categories 46.406 and 46.407 above in item 104).

The permission of only one parent will be sought (acceptable for categories 46.404 or 46.405). If marked, provide justification:

96. Assent of Children (*check one only*):

The assent of each child who is capable of providing assent based on age, maturity, and psychological state will be sought.

The assent of each child will not be sought because the capability of all of the children in this study population is so limited that they cannot reasonably be consulted. Explain why the capacity is so limited, e.g., age, maturity and/or psychological state:

The assent of each child will not be sought because the intervention or procedure involved in the research holds out a prospect of direct benefit that is important to the health or well-being of the children and is available only in the context of the research. Explain what the direct benefit may be and why it is only available in the context of the research:

Section 14 – Other

97. Please describe any other study procedures not referenced in the previous sections:

Not applicable
